## 5.0 Study Procedures

### 5.1 Data to be obtained from the VIOLET parent study

The VIOLET parent study has collected patient demographics, home medications, including vitamin D and calcium supplementations, Sequential Organ Failure Assessment (SOFA) Score to day 7, Lung Injury Prediction Score (LIPS), calcium levels, Charlson Comorbidity Index, duration of mechanical ventilation, and ARDS status. These data were obtained through patient/caregiver interview and medical record review. The SOFA score is a marker of illness severity and estimates risk of mortality. It quantifies CNS, respiratory, cardiovascular, hepatic, renal, and coagulation dysfunction/ failure and ranges from 0 to 24 (>90% risk of ICU mortality). ARDS was determined by local review of daily ventilator status/settings, PaO2 and SpO2 values,

and chest x-ray. These data will be obtained from the PETAL Clinical Coordinating Center at Massachusetts General Hospital.

### **5.2. Data to be collected specifically for VIOLET-BUD (Table 1)**

The primary outcomes for VIOLET-BUD are long-term global cognition and executive function. Only patients who have LC-MS confirmed Vitamin D deficiency (plasma 25-OHD < 20 ng/dL) at enrollment will have their outcomes determined. All outcome assessments will be blinded to treatment group. We will use comprehensive neuropsychological assessment which allows for detailed evaluation of specific cognitive domains. Prior work suggests Vitamin D deficiency predominantly affects short-term and working memory, attention, and executive function.

Long-term global cognition will be assessed for using the ***Repeatable Battery for the Assessment of Neuropsychological Status (RBANS, 30 min, Appendix C)***, which we have extensively used in our prior work. The RBANS is a comprehensive neuropsychological battery for the evaluation of global cognition and has been validated in subjects with mild cognitive impairment, moderate to severe traumatic brain injuries, vascular dementias, and Alzheimer's disease. In addition to providing a score for global cognition, it also provides individual scores for immediate and delayed memory, attention, visuospatial construction, and language.

To quantify executive function, we will use tests from the ***Delis-Kaplan Executive Function System (D-KEFS)*** which is the most definitive executive functioning battery in existence. Executive functioning refers to a wide array of "higher order" abilities that exist across a spectrum of cognitive sub-domains. Recent factor analyses have suggested that the majority of executive sub-domains fall broadly under conceptual flexibility, inhibition, and monitoring. As such, we have selected tests of executive functioning from the D-KEFS to assess these three broad abilities – ***the DKEFS Proverbs subscale (conceptual flexibility, 5 min, Appendix D), the DKEFS Trail Making-Number/Letter Switching subscale (inhibition, 2 min, Appendix E), and DKEFS Verbal Fluency Category Switching subscale (monitoring, 3 min, Appendix F)***. An executive function composite score will be calculated from these three DKEFS subscales.

The RBANS and executive function tests will be conducted by experienced neuropsychologists from the Vanderbilt ICU Delirium and Cognitive Impairment Study Group via videophone-assisted neuropsychological testing. Eight to 26 months post-randomization, study participants will return to their local study site where they were originally enrolled. At the local study site, there will be a trained proctor (research nurse or research assistant) with the patient to provide on-site support and assist the neuropsychologist rater (e.g., hand the appropriate instrument to the patient). To minimize the risk of poor connectivity, computers will connect to the internet using a local area network (LAN) connection rather than a wireless device. In the rare event of a poor internet connection, we have developed specific contingency plans and protocols (e.g., training the proctors to administer portions of the neuropsychological tests) to overcome any connectivity issues.

Study Assessment	Description	Source	Length
Past history of dementia or is on an acetylcholinesterase inhibitor medication (galantamine [Reminyl], Donepezil [Aricept] and rivastigmine [Exelon]) prior to randomization	This will be used to characterize the presence of pre-existing cognitive impairment.	Medical record	5 mins
Age, race, ethnicity sex, level of education, region of residence, and highest occupation 	These data will be used to estimate premorbid intelligence using an actuarial formula.	Informant or patient	5 mins
Repeatable Battery for the Assessment of Neuropsychological Status (RBANS, Appendix C). 	This neuropsychological battery will quantify long-term global cognition which is our primary outcome. It assesses immediate and delayed memory, attention, visuospatial construction, and language.	Patient	30 mins
Delis-Kaplan Executive Function System (D-KEFS) Proverbs subscale (conceptual flexibility, Appendix D), the DKEFS Trail Making-Number/Letter Switching subscale (inhibition, Appendix E), and DKEFS Verbal Fluency Category Switching subscale (monitoring, Appendix F). 	This neuropsychological battery will be used to quantify long-term executive function which is our primary outcome. It assesses conceptual flexibility, inhibition, and monitoring which are the cornerstones of executive function.  An executive function composite score will be calculated from these three DKEFS subscales.	Patient	10 mins
Katz Activities of Daily Living (ADL, Appendix G) 	Quantifies basic ADLs -- bathing, dressing, toileting, transferring, continence, and feeding.	Informant or patient	5 mins
Lawton Instrumental Activities of Daily Living Scale (IADL, Appendix H) 	Quantifies the patient's IADLs such as his/her ability to use the telephone, shopping, food preparation, housekeeping, laundry, transportation, medication management, and finances.	Informant or patient	10 mins
Outcomes After Critical Illness and Surgery (OACIS) Employment Status Questionnaire (Appendix I) 	9-item survey that characterizes the patient's baseline (prior to the critical illness) and current level of employment (full, partial, or not employed).	Informant or patient	10 mins
Death	While attempting patient contact, we will determine death status. If the patient died before the long-term follow-up, we will record date of death.	Medical record, informant, obituary web searches, or National Death Index	5 mins
Nursing Home Placement	During patient contact, we will determine if the patient placed in a nursing home. The date of placement will be recorded.	Medical record, patient, informant	5 mins

**Table 1.** VIOLET-BUD data to be collected by the local study team. The gray cells indicate data collected during the long term (8 to 26 month) follow-up visit and should take approximately 70 minutes.

Several studies have found results for neurocognitive testing to be very similar when assessments are completed by videoconferencing and by face-to-face evaluations. Galusha-Glasscock et al. observed that the videoconference-assisted RBANS, our primary cognitive measure, was highly correlated with the in-person RBANS with a correlation coefficient of 0.88 (p-value < 0.0001) in patients with and without dementia.

The local study team will also collect other long-term secondary outcome measures: functional status as measured by the Katz activities of daily living (ADL) scale and Lawton instrumental activities of daily living (IADL) scale, employment as measured by the Outcomes After Critical Illness and Surgery (OACIS) Employment Status Questionnaire, nursing home placement, and death.

For subjects who are unable to come to the local site for the long-term follow-up visit (e.g., due to mobility issues), the local site local study team will have the option to conduct the visit at their place of residence. To perform the videophone-assisted neuropsychological testing at the subject's resident, the study team will connect their laptop to the subject's local area network via wireless or ethernet connection. The local site study team may also use a mobile hotspot with a 4G LTE signal to perform the videophone-assisted neuropsychological testing.

VIOLET-BUD will also collect whether or not a patient has a past history of dementia or is on an acetylcholinesterase inhibitor medication (galantamine [Reminyl], Donepezil [Aricept] and rivastigmine [Exelon]) from the medical record. This will help determine if the patient has a history of pre-existing cognitive impairment prior to randomization. The determination of pre-existing cognitive impairment via medical record review will also be conducted in VIOLET subjects who were enrolled at the local site but died prior to the long-term outcome assessment or refused follow-up visit. These data will allow us to conduct survivor average causal effect (SACE), which will help determine the extent in which the competing of risk of death biased our findings

To facilitate merging of data sets, VIOLET-BUD participants will be assigned the same unique identification number as assigned in VIOLET. All VIOLET-BUD data will be entered into a secure REDCap database. Because the written and drawing portions of RBANS and executive function assessments need to be scored by the Vanderbilt ICU Delirium and Cognitive Impairment neuropsychologists, the local study team will upload these forms to the REDCap database.

## 6.0 Risks

This is a minimum risk study since there is no intervention. The Vitamin D intervention and safety monitoring has already been conducted as part of the VIOLET parent study. The VIOLET-BUD ancillary study will obtain long-term data using neuropsychological testing and survey instruments. For VIOLET-BUD specifically, subjects will undergo a neuropsychological examination at 8 to 26-months that can take approximately 40 minutes to perform. There is a small risk that a patient enrolled in VIOLET-BUD may become fatigued or distressed during the study neuropsychological assessments. In these cases, we will immediately stop the assessment and give the patient an opportunity to rest. Afterwards, we will ask the patient if we can continue with the neurocognitive assessments or if we should reschedule the long-term (8 to 26) follow-up appointment. Occasionally, patients and their families may get visibly frustrated and

distressed if the patient is unable to perform the cognitive tasks. We will reassure them that these tasks can be difficult to perform, and that such difficulties are common. If the patient or his or her family continue to be distressed after this reassurance, we will skip that particular task or stop the assessment altogether.

After the neuropsychological assessments, we administer surveys to the patient or authorized surrogate to collect additional data about the patient's functional status, baseline and current employment, education, region of residence, and highest occupation. These surveys will take an approximately 30 minutes to collect. If the patient is completing the surveys and becomes fatigued, then we will give the patient an opportunity to rest. If the patient can't continue with the survey, then we will attempt to get the survey data by phone at a later date.

Because patient identifiers are accessed throughout all phases of the study, there is a small risk of loss of patient confidentiality. Federal regulations at 45 CFR 46 111 (a) (7) requires that when appropriate, there are adequate provisions to protect the privacy of subjects and to maintain the confidentiality of data. To maintain confidentiality, all evaluation forms and reports will be identified only by a coded number. The same coded number will be used for subjects enrolled in both VIOLET and VIOLET-BUD. All related participant study records will be kept in a locked, password protected computer. The coded number will be generated by a computer at the PETAL CCC, and only the study team will have access to the codes. All records will be kept in a locked, password protected computer. All computer entry and networking programs will be done with coded numbers only. All paper case report forms will be maintained inside a locked office. Study information will not be released without the written permission of the patient, except as necessary for monitoring by the Vanderbilt Clinical Coordinating Center.

## **7.0 Reporting of Adverse Events or Unanticipated Problems involving Risk to Participants or Others**

As this is a non-intervention study, we do not anticipate having any adverse events. However, should any occur, they will be reported to the IRB per institution policies and procedures.

## **8.0 Study Withdrawal/Discontinuation**

If patient or caregiver declines participation at the outset or does not meet inclusion criteria, they will not be included in the study. If patients wish to discontinue taking part in the study, they will be instructed to contact local site principal investigator or the research staff and let them know that they wish to withdraw. At that time, no further data will be collected on the patient. All health data previously collected before they withdraw their consent will still be used for reporting and research quality.

## **9.0 Statistical Considerations**

We will determine if single, high-dose enteral Vitamin D treatment improves long-term global cognition and executive function compared with placebo using multiple linear regression. One model will be constructed for long-term RBANS and another for long-term executive function. We will use multivariable linear regression over unadjusted analyses because it is hypothesized that there will be a 5% absolute risk reduction in death for those who receive enteral Vitamin D. This may imbalance potential confounders between the treatment and placebo groups. Additional imbalances may

occur because of random chance. Multivariable regression will minimize this bias and lead to moderate gains in power.

The models will be adjusted for the covariates listed in **Table 2**. Nonlinear predictor effects for continuous variables will be incorporated into the models. If necessary, non-normally distributed continuous variables will be transformed. To account for correlation within a center, we will use robust standard errors.

In the event of significant missing covariate data, *multiple imputation* will be considered.

Multiple imputation will also be performed if portions of the cognitive assessments are missing; patients with completely missing cognitive data will be excluded from the study. Because several of our covariates (e.g., premorbid cognition and intelligence) may be highly correlated, we will assess for collinearity using variance inflation factors and use only one of those variables if a high degree of collinearity is observed. The final models will be validated using bootstrap internal validation and cross validation approaches. After the initial analysis has been completed, we will also evaluate if there is any effect modification of age, dementia status (medical record), baseline severity of illness (SOFA), mechanical ventilation status, and ARDS status. We will also perform a sensitivity analysis where death within the follow-up window will be considered equivalent to the worst cognitive outcome. This will be performed to further determine the effect of death on our findings.

Secondary analyses will be performed where we will determine how Vitamin D treatment affects the individual RBANS cognitive domains (e.g., immediate and delayed memory, attention, visuospatial construction, and language). We will also determine if treatment significantly improves long term functional status, employment as measured by the ICAP survey, nursing home placement, and death.

To estimate our sample size requirements, we used half a standard deviation (SD) of that particular test to define the minimum clinically important difference (MCID) threshold. Based upon the preliminary studies, the SD for the RBANS was 12. As a result, we considered a 6-point difference to be the MCID threshold for the RBANS. Based upon a two-sided alpha of 0.05 and 81% power, we will need outcome data in a total of 140 patients (~70 patients in each group) to detect a 6-point difference in RBANS between treatment groups. This sample size is feasible to obtain over 10 months. From September 2017 to July 2018, the six VIOLET-BUD sites enrolled 339 patients in VIOLET. Based upon the BRAIN-ICU study, we anticipate that 99% will not be deaf or blind, 62% will survive and 75% will follow-up at 8 to 26 months. We have the potential to enroll 155 patients making our required sample size of 140 patients very achievable. For our executive function composite score, the SD was 2.34 (**Section C6**), so the MCID threshold would be a 1.17 point difference. If we complete long-term executive function assessments on 140 patients as planned, we will have 81% power to detect this 1.17-point difference in the executive function composite score assuming a two-sided alpha of 0.05.

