### **4.0 Enrollment/Randomization**

Because VIOLET-BUD is an ancillary study to the VIOLET parent study, randomization to the Vitamin D3 versus placebo group has been completed. The PETAL Clinical Coordinating Center performed computerized randomization using 1:1 allocation stratified by enrolling hospital. For VIOLET-BUD, the site research and clinical staff, patient and authorized surrogate will be blinded to treatment assignment.

VIOLET-BUD will enroll patients from 7 (out of 42) PETAL sites that participated in VIOLET. The local site will contact all patients who were enrolled in VIOLET to recruit patients for VIOLET-BUD. As part of the VIOLET parent study's informed consent document, participants agreed to be contacted for future studies. Although the patient contact will typically occur by phone, the initial method of contact may occur by e-mail, letter, or text depending on patient preferences or availability. To maximize the feasibility of the study, the long-term follow-up assessments conducted between 8 and 26 months) after randomization will be allowable. Patients enrolled in VIOLET will be contacted consecutively.

Once a VIOLET patient has been contacted, the local site study coordinator will use a phone or e-mail script (**Appendix A**). He/she will describe VIOLET-BUD's study protocol in lay terminology over the phone. It will be emphasized that the data collected will be for research purposes. The research staff will inform the patient that there is no obligation to

participate in the study. If the patient refuses to participate in VIOLET-BUD or died prior to the long-term follow-up, then this will be recorded. If the patient cannot follow-up because they reside in a skilled nursing facility or has significant mobility issues, lives too far from the local site, cannot obtain transportation to the local site, is incarcerated, or is too cognitive impaired to participate, then this will be recorded.

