## D5.2. Sample Size Calculations

In our original sample size calculations, we used half a standard deviation (SD) of that particular test to define the minimum clinically important difference (MCID) threshold. The SD for the RBANS in our population from previous studies was 12.4. Thus, we considered a 6-point difference to be the MCID threshold for the RBANS. Based upon a two-sided alpha of 0.05 and 80% power, we computed that we would need outcome data in a total of 140 patients with completed follow-up data (~70 patients in each group) to detect a 6-point difference in RBANS between treatment groups. However, VIOLET-BUD enrolled 95 patients; because the VIOLET parent trial stopped enrollment early, no additional patients could be recruited for this ancillary study. However, this sample size still provides us with more than 80% power to detect at least a

7.2-point difference. Some have considered an RBANS difference of 8 points to be the MCID threshold. For our executive function composite score, the SD in our previous population was 2.34. With 95 patients assessed, we will have greater than 80% power to detect a 1.4-point difference in the executive function composite score assuming a two-sided alpha of 0.05.

For our multiple linear regression models, we will have one degree of freedom available for every 10 to 15 patients with completed outcome measurements. Consequently, we will be able to accommodate 9 degrees of freedom for our multivariable models without overfitting.

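### The protocol's 81% power with 140 patients does not follow from its printed inputs: both primary outcomes are set at exactly half an SD, which gives about 84%

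*Protocol*

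**What the plan says.** Section 9.0 of the protocol fixes the effect size by a single rule: "we used half a standard deviation (SD) of that particular test to define the minimum clinically important difference (MCID) threshold".

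- **RBANS.** The protocol reports that "the SD for the RBANS was 12" and continues: "we considered a 6-point difference to be the MCID threshold for the RBANS". It then says: "Based upon a two-sided alpha of 0.05 and 81% power, we will need outcome data in a total of 140 patients", with roughly "70 patients in each group".
- **Executive function composite.** The SD is 2.34 and the threshold 1.17 points. With 140 assessed, "we will have 81% power to detect this 1.17-point difference in the executive function composite score", again at two-sided alpha 0.05.

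Section 4.0 of the protocol describes the parent trial's randomization as "using 1:1 allocation stratified by enrolling hospital", so equal groups are the natural reading.

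Section D5.2 of the SAP gives its own account of the original RBANS calculation. It keeps 6 points and 140 patients, but states 80% power and a different SD: "The SD for the RBANS in our population from previous studies was 12.4". For executive function it repeats the SD of 2.34 and gives power only for the 95 patients actually enrolled.

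**The concern.** Under the half-SD rule the standardized difference is 0.5 for both outcomes, whatever the SD. Two calculations with the same standardized difference, alpha and group size must give the same power. They do agree with each other in the protocol, but on a value that 0.5 SD with 70 per group does not produce. The two documents also print different SDs and different powers for one and the same RBANS calculation.

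What is at stake is whether a reader can reproduce the planned sample size. Target number and power are the figures that justify a design, and here they are given for both primary outcomes. No analysis or decision in the SAP depends on the discrepancy.

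**Working it through.** **Inputs**

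| Quantity | Value | Source |
|---|---|---|
| Alpha | 0.05, two-sided | Protocol 9.0 |
| Patients with outcome data | 140, about 70 per group | Protocol 9.0 |
| RBANS difference and SD | 6 and 12 | Protocol 9.0 |
| Executive function difference and SD | 1.17 and 2.34 | Protocol 9.0 |
| RBANS SD for the original calculation | 12.4 | SAP D5.2 |

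The 140 counts patients with outcome data, so attrition cannot account for a gap.

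**Formula.** With n per group, difference δ and SD σ, the noncentrality is λ = (δ/σ) × √(n/2). Normal-approximation power is Φ(λ − 1.960). The exact figure uses the noncentral t distribution with 2n − 2 = 138 degrees of freedom.

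**Step 1: the protocol's inputs**

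- RBANS: 6/12 = 0.5. Executive function: 1.17/2.34 = 0.5.
- λ = 0.5 × √35 = 2.958.
- Normal approximation: Φ(2.958 − 1.960) = Φ(0.998) = 84.1%.
- Exact t: 83.6%.

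The stated 81% is not reproduced for either outcome. The gap is 2.6 points (exact t) or 3.1 points (normal).

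**Step 2: the number needed for 81% at 0.5 SD**

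- Normal approximation: n = 2 × (1.960 + 0.878)² / 0.5² = 64.4, so 65 per group, 130 in total.
- Exact t: 65 per group gives 80.8%, 66 gives 81.4%. The total is 132.

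Against the stated 140 this is an excess of 8 to 10 patients.

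**Step 3: the SAP's RBANS SD**

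- 6/12.4 = 0.484, so λ = 0.484 × √35 = 2.863.
- Normal approximation: Φ(2.863 − 1.960) = Φ(0.903) = 81.7%. Exact t: 81.1%.
- The exact-t total for 81% is 70 per group, or 140.

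This reproduces the protocol's RBANS figure. The SAP's 80% is also tenable on this SD: 138 patients give 80.6%, and 140 exceed the target slightly.

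**Step 4: can rounding rescue the executive function figure?**

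- Least favourable limits: 1.165/2.345 = 0.497, exact t power 83.1%.
- Most favourable limits: 1.175/2.335 = 0.503, exact t power 84.0%.

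It cannot. For 1.17 points to have 81% power, the SD would have to be about 2.42, whereas both documents print 2.34.

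**The case against.** The strongest reply is that the authors may have built in an allowance that they did not print. Section 9.0 plans robust standard errors for correlation within centers. A design effect of 1.07 takes 0.5 SD with 70 per group to 81.0%, for both outcomes at once; with an assumed 20 patients per site, that is an intraclass correlation of about 0.004. A rank-test efficiency of 0.955 gives 81.8%, and so does a 55:85 split. Adjustment for 12 further model degrees of freedom does not explain the gap, since power stays at 83.5%. The protocol's calculation mentions none of these allowances, and it states near-equal groups and plans linear regression. The printed inputs therefore still do not give the printed power.

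The reply does limit how far one may go. A reader might infer that the RBANS power was computed with 12.4 and then copied to the executive function line. That is plausible, but the documents do not show it. A common allowance would also yield equal powers, and the section cited for the executive function SD (C6) is not part of this protocol. Nor can one say that 12.4 is the only route to 81%; it is the only one among the SDs that the documents state.

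It is also fair to say that events have overtaken the figure. The SAP replaces the planning figures with those for 95 patients and attributes the shortfall to the parent trial, not to this calculation. That stands, and it is a reason to rank the point low. It does not make the protocol's figures correct or reconcile them with the SAP's account of the same calculation.

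**Conclusion.** Wrong as written, and minor. On the printed inputs, 140 patients give 83.6% power (84.1% by the normal approximation), not 81%, for both primary outcomes, and 81% would need 130 to 132. For RBANS a likely explanation is available: 12 may be 12.4 rounded. For executive function the documents offer none.

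The conclusion assumes a two-sample comparison of means with equal groups, independent patients and no covariate gain, because the protocol states nothing else in its calculation.

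Two stronger readings should be resisted. The trial is not underpowered because of this error, which is conservative: the stated inputs give more power than claimed. The excess is also not 12 patients. That figure compares 140 with the 128 needed for 80% power, which is not the power the protocol claims.

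**What to change.** Make three corrections, in a clarifying note to section 9.0 of the protocol or in the methods of the final report, since enrollment has closed:

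1. Restate the executive function power for 140 patients and 1.17 points as about 84%.
2. For RBANS, give the SD actually used. Either keep SD 12 with 6 points and state about 84%, or use SD 12.4 with 6 points and 81%. In the second case, say that half of 12.4 is 6.2 and was rounded to 6; otherwise 6 points departs from the half-SD rule.
3. Make section 9.0 of the protocol and section D5.2 of the SAP agree on the SD and power of the original calculation, which now read 12 and 81% in one, 12.4 and 80% in the other.

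If an allowance such as a design effect was in fact applied, state it and its value instead. The cost is a few figures and a sentence. No design element, analysis or data collection changes.
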